The Blood Transfusion Services are able to unblind for the clinical treatment of a patient. Please refer to the site Standard operating procedure for more details of this process. If a patient's treatment is unblinded before the 24 hour primary end point their data will not be used in the analysis.

STATISTICS

Sample size

The primary outcome of interest will be overall need for blood transfusion at 24hr after surgery (including all used blood components from the start of surgery). For the sample size calculations G*Power version 3.1.2 was used.

Based on the available literature ^{9,10,12}, the investigator hypothesized a 70-90% reduction in total units of blood products in the group receiving fibrinogen compared with the group receiving conventional therapy. An estimate of blood product requirement in the group receiving conventional therapy is mean 3.4 units (standard deviation 5.9) based on our data from 2005 to 2007 for AVR+CABG, MVR+CABG, AVR+MVR, and Aortic root repair +/-AVR. Standard deviation 5.9 was used for both groups. Blood product requirement in the two groups will be compared using the Mann-Whitney U test for two independent samples. The sample size calculation was based on a two-tailed test with $\alpha = 0.05$, for $\beta = 0.2, 0.1, \text{ and } 0.05$. The sample sizes shown Table 1 represent the number of patients required in each group.

Details of the planned analysis

~~Individual case forms will be completed by the research coordinator for individual patients.~~ **The research coordinator will complete individual case forms for individual patients.** These forms will be detailing demographic characteristics,

Capital Health

intra-operative, post-operative and follow-up outcomes. Outcome data and blood samples will be collected according a lab/data schedule (Table 2). ~~All data will be reviewed by the appropriate clinical outcomes committee.~~ **The Sponsor will review all data.** Once reviewed all data will entered and maintained electronically.

Primary outcome: Blood component requirement in the two groups will be compared using the Mann-Whitney U test for two independent samples.

Secondary outcomes: Univariate comparisons between patients randomized to FIB and patients randomized to PLACEBO group will be carried out based on pre-, intra-, and post-operative variables using Chi-square tests for dichotomous variables, two-tailed t-tests for continuous variables and Wilcoxon rank sum tests for nominal variables.

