All statistical analyses will be performed at the QEII Health Sciences Center using SAS version 9.2 (Cary, North Carolina). Data validation will be an integral part of this protocol and will be carried out using already established clinical and administrative patient databases available through the Division of Cardiac Surgery at the QEIIHSC. This will ensure 100% follow-up of all patients and data accuracy. ~~All discrepancy will be investigated by the clinical outcomes committee.~~ **The Data and Safety Monitoring Committee will investigate all discrepancies.** The Maritime Heart Center (MHC) cardiac surgery database is a prospectively collected, clinical database that captures detailed information on a wide range of pre-operative, intra-operative, and in-hospital post-operative variables including post-operative complications and in-hospital mortality for all patients undergoing cardiac surgery at the QE II Health Sciences Center. It is audited on an annual basis to ensure reliability of data capture. The MHC cardiac surgery database will be linked to the Canadian Institute for Health Information (CIHI) Discharge Abstract Database and the Nova Scotia Vital Statistics database through the Population Health Research Unit (PHRU) at Dalhousie University. The CIHI Discharge Abstract Database is a national administrative database that contains extensive data on all admissions to hospital and enables us to track all

Capital Health

readmissions to hospital. The Nova Scotia Vital Statistics database collects information on all deaths occurring within the province of Nova Scotia and enables us to track all-cause mortality following discharge from hospital. The following data will be obtained from the MHC-PHRU data link after 6-months follow-up for all patients:

- i) Cardiac related mortality
- ii) Readmission to hospital for acute myocardial infarction (AMI), acute coronary syndrome (ACS), or congestive heart failure (CHF)
- iii) Re-intervention including CABG and/or PCI

Estimated Recruitment Rate

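### The primary analysis gives a p-value only: no estimate or interval for the reduction in mean units on which the trial was sized, and no adjustment for baseline values already measured

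*Combined protocol and SAP*

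**What the plan says.** Under Details of the planned analysis: "Primary outcome: Blood component requirement in the two groups will be compared using the Mann-Whitney U test for two independent samples". The Sample size section names the same test. For secondary outcomes the plan is "Univariate comparisons between patients randomized to FIB and patients randomized to PLACEBO group", by chi-square, t and Wilcoxon tests. No regression model, stratified test, covariate, effect estimate or confidence interval appears in the document. The only further statement is that the final analysis will take the interim analysis into account.

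The sizing is on the mean scale. The control arm is taken as "mean 3.4 units (standard deviation 5.9) based on our data from 2005 to 2007", "Standard deviation 5.9 was used for both groups", and "the investigator hypothesized a 70-90% reduction in total units of blood products". Table 1 expresses each column as a change in mean units; the 70% column is 3.4 to 1.0. The planned total of 222 is twice the 111 in its 80% power row.

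Table 2 schedules preoperative hemoglobin and fibrinogen for all patients. Procedure type can be inferred from the inclusion criteria. It should also be in the cardiac surgery database, which "captures detailed information on a wide range of pre-operative" and intra-operative variables, but neither Table 2 nor the data form lists it as an item.

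**The concern.** There are two separate gaps.

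**Estimate.** The primary objective is to determine how many units are used, and the sample size rests on a change in the mean. A Mann-Whitney test shows whether one arm tends to use fewer components, not by how much. As planned, the trial could be significant and still not say whether use fell by 30% or by 70%.

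**Adjustment.** The population mixes double procedures, redo-sternotomies and root repairs. The documents give reasons to expect baseline values to predict component use. They call fibrinogen the limiting factor for postoperative hemostasis. Red cells are given below a hemoglobin of 70 g/l. The quoted transfusion rate is 38% across all cardiac cases and 60% for AVR+CABG. The randomization section describes no stratification, so any chance imbalance would pass unadjusted into the result.

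**Working it through.** **1. The plan's own figure.** Inputs from Sample size and Table 1: difference 2.4 units, SD 5.9 in both arms, two-sided alpha 0.05, power 80%; 1:1 allocation assumed because 2 × 111 = 222.

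- Two means, normal approximation: n = 2 × (1.960 + 0.842)² × (5.9/2.4)² = 2 × 7.85 × 6.04 ≈ 95 per group; noncentral t gives 96.
- Dividing by the minimum asymptotic relative efficiency of the Mann-Whitney test: 96/0.864 = 111. This matches Table 1.
- The nine cells in the 30%, 50% and 70% columns reproduce exactly; the three in the 90% column come out 2 lower than printed.

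The 80% power therefore already belongs to the unadjusted test.

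**2. What a rank-based summary would show.** The shape of the unit counts is not given, so I assume negative binomial with the stated mean and SD.

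- k = 3.4²/(5.9² − 3.4) = 11.56/31.41 = 0.368.
- Controls with zero units: (0.368/3.768)^0.368 = 42%. The control median is 1.
- Treated with zero units, same k: 50% reduction (mean 1.7), (0.368/2.068)^0.368 = 53%; 70% reduction (mean 1.02), (0.368/1.388)^0.368 = 61%. The treated median is 0 in both cases.

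The difference in medians is 1 under either reduction, so it cannot tell them apart. In a negative-binomial simulation with a baseline covariate (1,000 trials per setting), a true mean reduction of about 2.4 units gave an average Hodges-Lehmann shift of only 0.5 to 0.9.

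**3. What a mean-based estimate would show.** With the plan's SD, an unadjusted mean difference has a 95% half-width of 1.96 × 5.9 × √(2/111) = 1.55 units, against the 2.4 used for sizing. Under the model in step 2 with a true 70% reduction (ratio 0.30), the bootstrap 95% CI for the ratio of means averaged about 0.19 to 0.49.

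**4. What adjustment would add.** Simulated trials used the counts in step 2, 111 per arm and one baseline covariate linked to each patient's underlying transfusion rate. They compared the Mann-Whitney test with a rank analysis of covariance. The rank correlation of covariate with outcome is an assumption.

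| True reduction | Mann-Whitney power | Gain, rank corr. 0.14 | 0.26 | 0.46 |
|---|---|---|---|---|
| 50% | about 60% | about 0 | 2-3 points | 7-10 points |
| 60% | about 82% | about 0 | 2-3 points | 7-10 points |
| 70% | 96-97% | 0-2 points over the whole range | | |

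Type I error of the adjusted test was 3.9% to 5.5% across the runs. Each power figure carries a simulation standard error of about 1 point (for example √(0.6 × 0.4/2,500) = 0.0098).

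**5. Why 96-97% and not 80%.** Table 1 keeps the SD at 5.9 even when the mean falls to 1.0. In the count model the treated SD at mean 1.02 is √(1.02 + 1.02²/0.368) = 1.96, so the arms separate more clearly. If Table 1's own formula is kept and the SD replaced by 5.9 × √(1 − R²), power at 111 per arm goes from 80.0% to 80.8% (R² 0.02), 84.0% (0.10), 88.0% (0.20) and 91.8% (0.30).

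**The case against.** The strongest reply is that nothing here is an error. An unadjusted rank test in a randomized trial is valid; chance imbalance does not inflate its type I error, and the sample size is right for it. All of that stands. A reader might infer from the missing covariates that the trial falls short of its stated 80% power. Step 1 shows that it does not.

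The gain from adjustment may also be small. Eligibility narrows both laboratory covariates: hemoglobin below 110 is excluded, and fibrinogen must lie between 1.0 and 3.8 g/l. A weak correlation is therefore plausible. At the 70-90% reduction the plan hypothesizes, the count model leaves little room for improvement. This also stands, and it limits the adjustment point to the case where the true effect is smaller than planned.

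Three further limits apply. The simulations used a single covariate, not several. Procedure type is implied rather than listed, and the eligibility categories overlap, since a redo-sternotomy can also be an AVR+CABG. Finally, a reader might infer that adjusting the test would itself supply the missing estimate. It would not: a rank analysis of covariance gives a difference in ranks and a proportional-odds model gives an odds ratio. The estimate has to be specified separately, and it needs no covariates.

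None of this answers the missing estimate. The document names no measure of how large the reduction is.

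**Conclusion.** The point holds in two parts of unequal weight.

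The firmer part is that the plan specifies no estimate or interval for the quantity it was sized on. This rests on the text alone. That medians or a shift would not fill the gap rests on the assumed negative-binomial shape with the plan's mean and SD.

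The lesser part is that baseline adjustment is available at almost no cost and is not used. It forgoes a possible gain: about 0-2 points of power at a 70% reduction, and 0 to 10 points at 50-60%, for rank correlations from 0.14 to 0.46. Table 1's constant-SD formula would put the gain at the design effect higher, at about 1 to 12 points for R² of 0.02 to 0.30. The documents do not settle covariate strength, so only a range can be stated. They do not support a claim that planned power is lost or that the unadjusted test is biased.

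**What to change.** 1. Pre-specify the ratio (or difference) of mean units from the start of surgery to 24 h after study drug, with a bootstrap 95% CI, as the primary effect estimate.
2. Make the primary test a rank analysis of covariance adjusted for preoperative hemoglobin and preoperative fibrinogen. Add procedure type only if it is taken from the surgical database with non-overlapping categories defined in advance.
3. Keep the unadjusted Mann-Whitney test as a sensitivity analysis.
4. Fix the estimator, covariates and coding in writing before the unblinding at 110 participants listed under Unblinding.

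The cost is analysis-plan wording, one model and a bootstrap in SAS, and a coding rule for procedure type if it is used. Hemoglobin and fibrinogen need no new data, and the sample size need not change. The downside is that covariates and their coding must be settled in advance and cannot be revised after unblinding.

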After eligibility and written informed consent is confirmed patients will be randomized on the day of surgery after arrival at the OR to receive either fibrinogen concentrate or placebo after heparin reversal as indicated in the algorithm (Figure 3). If the patient has a diffuse medical bleed then the research coordinator will be called to inform The research coordinator study drug designate will call the study drug designate to randomize the patient and a sequential envelope will be opened by them in the blood bank. The drug/placebo will be prepared in the Blood Transfusion Services at the Infirmary site. The drug/placebo will be transported to the OR by the study drug designate.

Dosage and Dosage Regimen

The dose of fibrinogen concentrate will be calculated based on the point of care measurement of maximum clot firmness (MCF)

Capital Health

in the FIBTEM® test performed on CPB (aortic cross clamp off)¹⁰. According to the available literature we will use the following formula to achieve the preoperative (baseline) FIBTEM MCF (mm):

$$\text{Fibrinogen dosage (g)} = [\text{Preop FIBTEM MCF (mm)} - \text{FIBTEM MCF (mm)}] \times \text{bodyweight (kg)} \times c$$

$$C = \frac{0.5 \text{ g}}{1(\text{mm}) \times 70}$$

70

The formula can be simplified to:

$$(\text{Preop FIBTEM MCF} - \text{FIBTEM MCF}) \times \text{bodyweight}/140.$$

Calculation example: A patient's bodyweight is 75kg. The baseline FIBTEM MCF showed 22mm. The FIBTEM test on CPB shows a MCF of 10 mm. The overall dose of concentrated fibrinogen to achieve the baseline MCF of 22 mm would be:

$$\text{Fibrinogen dosage (g)} = (22 - 10) \times 75/140 = 12 \times 75/140 = \mathbf{6.4}$$

Fibrinogen dosing will be based on the results of the FIBTEM® analysis. The amount of fibrinogen concentrate corresponds to approximately 0.5 g of fibrinogen concentrate needed to raise MCF by 1 mm in a 70 kg patient^{9,10,26}. The maximum fibrinogen concentrate dose used in this study will be 10 g. If the baseline FIBTEM® is ≤ 12 mm the fibrinogen dosage will be calculated **from a minimum baseline value of 15 mm to achieve a more effective fibrinogen dosage**. In the placebo group, the standard hemostatic algorithm involving the use of plasma, Cryo and platelets (Figure 3), will be used as per the standard of care currently in place at CDHA.

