clinic at the time window of six weeks +/- 1 week, a phone visit will occur by the research coordinator. Additionally all patients will be contacted by a research coordinator at three and six months. The focus of the interviews will be to determine anginal symptoms, and ~~need for~~ **if** readmission to hospital for acute myocardial infarction (AMI), acute coronary syndrome (ACS) or congestive heart failure (CHF) **occurred**. Events of interest include: incisional wound infection, thrombosis, recurrent angina, myocardial infarction, angiography, percutaneous coronary intervention (PCI), repeat cardiac surgery, stroke and cardiac related mortality. Any patients with evidence of adverse study drug related events at follow-up will be investigated further by the Data and Safety Monitoring Committee to review all the supporting evidence.

Proposed frequency of analysis

As previously stated there will be an interim analysis performed by the data and safety monitoring committee. This analysis will be conducted when half of the patients have been enrolled. The final analysis will be conducted once all enrolled patients have reached their follow-up date. All final analysis will take into consideration that an interim analysis was conducted.

SELECTION AND WITHDRAWAL OF SUBJECTS

Inclusion criteria

Participants will be eligible to participate in this trial if they:

- are **scheduled for** elective complex cardiac surgical procedures including:
 - double procedures (aortic valve replacement (AVR)+CABG, mitral valve repair/replacement (MVR)+CABG, AVR+MVR),
 - redo-sternotomies, and
 - Aortic root repair +/-AVR.
- have a preoperative fibrinogen level of ≤ 3.8 g/l

Capital Health

Subject exclusion criteria

Participants will be excluded if they have:

- Any known congenital or pre-existing bleeding disorder,
- ~~pre-existing clinically significant abnormal fibrinogen levels~~
- ~~pre-existing clinically significant abnormal fibrinogen levels~~
- ~~pre-existing clinically significant abnormal FIBTEM MCF tests~~
- Preoperative fibrinogen level of < 1.0 g/l
- Preoperative FIBTEM[®] of < 5 mm
- Preoperative fibrinogen level of > 3.8 g/l
- severe liver disease (alanine aminotransferase or aspartate aminotransferase > 150 U/l),
- inability to provide informed consent,
- emergency surgery,
- **self-report** pregnancy or nursing,
- age under 18 years,

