- intake of anti-clotting drugs within 2-5 days preoperatively (low dose ASA is allowed) based on the drug's half life or pharmacokinetic profile,
- allergy to concentrated fibrinogen or other components in the product,
- anemia (Hb < 110),
- diagnosed deep vein thrombosis (DVT),
- pulmonary embolism,
- acute stroke **(within the last 3 months)**,
- acute myocardial infarction (within the last 3 months),
- **any unstable medical condition as determined by the Principal Investigator**
- **within the past 30 days, participated in or currently enrolled in a clinical trial.**

Subject withdrawal criteria

Capital Health

As per the intraoperative algorithm (Figure 3) the Anesthesiologist and the Surgeon complete a bleeding assessment ten minutes after the protamine is given. If the patient is not having a diffuse medical bleed they will not be randomized and will be considered a screen failure. **Patients who are experiencing surgical bleeding after weaning from CPB and protamine administration with requirement of a second pump run are withdrawn from the study.** In case of an ongoing bleeding after step 3 of the study algorithm (Figure 3) an immediate and blinded FIBTEM is performed in order to prevent an overdosing of fibrinogen. If the FIBTEM shows an amplitude > 20 mm the patient will be unblinded and drop out of the study for safety reasons. This way it is ensured that a patient who received concentrated fibrinogen is not getting Cryoprecipitate (step 4 of study algorithm; Figure 3) leading to supraphysiologic levels of fibrinogen. Patients who have extremely rare complications like air embolism, heart perforation or heart lung machine failure will be ~~excluded~~ **withdrawn** from the study.

TREATMENT OF SUBJECTS

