As per the standard of care in this surgical population, all post-operative cardiac surgery patients will be taken immediately to a dedicated cardiovascular intensive care unit (CVICU). All patients will receive respiratory and hemodynamic support as needed. Each patient will be required to meet standard hospital criteria both prior to extubation and prior to transfer to the intermediate-care unit (IMCU). Discharged patients will be transferred to an intermediate-care unit or general-care ward under the care of the same cardiac surgical team. All patients will be monitored continuously for a minimum of 24 hours. In case of a post-operative bleeding in CVICU the same algorithm (Figure 3) like in the OR will be used. In case of surgical bleeding a re-sternotomy will be performed. Diffuse bleeding will be treated with blood components (step 2 -5, Figure 3). Patients having a valve replaced with a mechanical valve will receive heparin or warfarin 48 hours after surgery. All other patients will get ASA (acetylsalicylic acid, Aspirin®, Bayer Canada) on the first postoperative day (anticoagulation protocol, Division of Cardiac Surgery, QEII, Halifax, Canada).

ASSESSMENT OF SAFETY

Adverse Events

The following treatment-emergent and adverse effects will be captured during this study from the date ~~the consent was signed~~ of randomization to the 6 month follow-up:

Treatment-emergent adverse events

- Pleural effusion
- Atrial fibrillation
- Postoperative Delirium
- Reoperation because of surgical bleeding and unknown bleeding
- Air embolism

Adverse events (A/E) and Serious adverse events (SAE)

- Anaphylaxis
- Stroke
- Myocardial infarction
- Pulmonary embolism
- Deep vein thromboembolism
- Sternal wound infection
- Recurrent angina
- Angiography
- Percutaneous coronary intervention (PCT)
- Repeated cardiac surgery
- Cardiorespiratory arrest
- Cerebral hemorrhage
- Death

All serious unexpected adverse drug reactions will be reported to Health Canada as per ICH/GCP guidelines.

Unblinding

Unblinding for this study will occur when:

1. Clinical treatment decisions need to be made and when an unexpected serious adverse event occurs and the intervention must be made known.
2. At the request of the Data Safety Monitoring Committee.

Capital Health

3. After 110 participants have reached the primary endpoint for interim analysis.
4. At the conclusion of the study to determine the effect of the intervention.

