CFT (clot formation time): time from initiation of clotting until a clot firmness of 20mm is detected
 => fibrin polymerisation, stabilisation of the clot with thrombocytes and F XIII

MCF (maximum clot firmness): firmness of the clot
 => increasing stabilisation of the clot by the polymerised fibrin, thrombocytes as well as F XIII

ML (maximum lysis): reduction of the clot firmness after MCF in relation to MCF
 => stability of the clot (ML < 15%) or fibrinolysis (ML > 15% within 1h)

Figure 2. FIBTEM® Test Specificities

[figure not shown]
[figure not shown]
FIBTEM:

- activation as in **EXTEM**
- platelet inhibition reagent added

TEMogram shows isolated fibrinogen contribution to Clot firmness

- A)
- **EXTEM:** amplitude low
 - **FIBTEM:** amplitude normal
- => fibrinogen level OK
=> platelet deficiency

- B)
- **EXTEM:** amplitude low
 - **FIBTEM:** amplitude low
- => fibrinogen deficiency

[figure not shown]
[figure not shown]

Figure 3. Treatment Algorithm

[figure not shown]

Table 1. Sample Size Calculation

	Relative Risk Reduction in Mean Number of Units Transfused			
Power = 1-beta	30% $\Delta = 1.0$ units (3.4 to 2.4)	50% $\Delta = 1.7$ units (3.4 to 1.7)	70% $\Delta = 2.4$ units (3.4 to 1.0)	90% $\Delta = 3.1$ units (3.4 to 0.3)
80%	634	220	111	69
90%	848	295	149	92
95%	1049	364	183	113

Table 2. Schedule of Assessments

	Preop I+II	Intraop I	Intraop II	Intraop III	Postop I	Postop II	Postop III	Postop IV
Time intervals	Baseline	On Bypass Aortic Clamp Off	Off Bypass After Heparin reversal (5-15 minutes post protamine)	10 minutes after administration (+5 minutes)	End of Surgery (+10 minutes)	Blood Draw 12 Hours (+60 minutes)	Blood Draw 24 Hours (+60 minutes)	Discharge
Primary Outcome					Total Blood Components Used	Total Blood Components Used	Total Blood Components Used	Total Blood Components Used
					Cryo Used	Cryo Used	Cryo Used	Cryo Used
					FFP Used	FFP Used	FFP Used	FFP Used
					Packed Red Cells Used	Packed Red Cells Used	Packed Red Cells Used	Packed Red Cells Used
					Platelets Used	Platelets Used	Platelets Used	Platelets Used
Secondary Outcomes	Fibrinogen Levels		Fibrinogen Levels	Fibrinogen Levels	Fibrinogen Levels	Fibrinogen Levels	Fibrinogen Levels	Adverse Effects
	Hematocrit		Hematocrit	Hematocrit	Hematocrit	Hematocrit	Hematocrit	Anaphylaxis

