	Hemoglobin	ABG/ Hemoglobin	ABG/ Hemoglobin	ABG/ Hemoglobin	ABG/ Hemoglobin	Hemoglobin	Hemoglobin	CVICU LOS
	INR/PT		INR/PT	INR/PT	INR/PT	INR/PT	INR/PT	Deep Vein Thromboembolism
	Platelet Count		Platelet Count	Platelet Count	Platelet Count	Platelet Count	Platelet Count	Hospital LOS
	PTT		PTT	PTT	PTT	PTT	PTT	
	*ACT	ACT	ACT	ACT	ACT		Blood Drainage	In Hospital Mortality
	*EXTEM	EXTEM	EXTEM	EXTEM	EXTEM	EXTEM	EXTEM	Myocardial Infarction
	*INTEM		INTEM	INTEM	INTEM	INTEM	INTEM	Pulmonary Embolism
	*FIBTEM	FIBTEM	FIBTEM	FIBTEM	FIBTEM	FIBTEM	FIBTEM	Stroke
			HEPTEM	HEPTEM	HEPTEM	HEPTEM	HEPTEM	
	AT III		Usage of Factor VII a	Usage of Factor VII a	Usage of Factor VII a	Usage of Factor VII a	Usage of Factor VII a	Usage of Factor VII a
	*ABG		Usage of human prothrombin complex	Usage of human prothrombin complex	Usage of human prothrombin complex	Usage of human prothrombin complex	Usage of human prothrombin complex	Usage of human prothrombin complex

Please Note: 24 hour blood draw = primary endpoint highlighted in green, assessments highlighted in peach are outside

*the standard of care ,
Preoperative 1- assessments done in Same day admission or on the floor the day prior to OR
Only these values will be done on the Preoperative II time point. Preoperative II (window is +10 minutes post art line insertion)

Table 2. Schedule of Assessments (continued)

Time intervals	6 week post operative clinic visit (+1week) (phone visit may occur if patient is not brought in within window)	3 month phone visit (+1week)	6 month phone visit (+1week)
Secondary Outcomes	
 • Angina • Re-admission (CHF, AMI, ACS) • Incisional wound infection • Thrombosis • MI • Angiography • PCI (percutaneous coronary intervention) • Repeat cardiac surgery • Cardiac Mortality 	
 • Angina • Re-admission (CHF, AMI, ACS) • Incisional wound infection • Thrombosis • MI • Angiography • PCI (percutaneous coronary intervention) • Repeat cardiac surgery • Cardiac Mortality 	
 • Angina • Re-admission (CHF, AMI, ACS) • Incisional wound infection • Thrombosis • MI • Angiography • PCI (percutaneous coronary intervention) • Repeat cardiac surgery • Cardiac Mortality

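### The laboratory and ROTEM secondary outcomes are compared without adjusting for the preoperative values that Table 2 already collects, which gives up some precision at no saving

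*Combined protocol and SAP*

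**What the plan says.** The only analysis text for secondary outcomes is one sentence in STATISTICS, Details of the planned analysis: "Univariate comparisons between patients randomized to FIB and patients randomized to PLACEBO group will be carried out based on pre-, intra-, and post-operative variables". It assigns chi-square tests to dichotomous variables, two-tailed t-tests to continuous variables, and "Wilcoxon rank sum tests for nominal variables". No ANCOVA, regression, change score or repeated-measures model is named anywhere. Preoperative values enter as variables to be compared between arms, not as covariates.

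Table 2 has a baseline column (Preop I+II) with entries for fibrinogen, hematocrit, hemoglobin, INR/PT, PTT, platelets, EXTEM, INTEM and FIBTEM. These are measured again 10 minutes after administration, at the end of surgery, and at 12 and 24 hours. HEPTEM has no preoperative entry; it starts at the draw labelled "Off Bypass After Heparin reversal (5-15 minutes post protamine". There are two preoperative draws. The note to the table describes the first as "Preoperative 1- assessments done in Same day admission or on the floor the day prior to OR" and the second as limited to certain values taken after arterial line insertion.

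The preoperative values have other uses. Fibrinogen and FIBTEM determine eligibility (for example, exclusion for "Preoperative fibrinogen level of > 3.8 g/l"), and Dosage and Dosage Regimen says "we will use the following formula to achieve the preoperative (baseline) FIBTEM MCF (mm".

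**The concern.** When the same quantity is measured before and after treatment, a t-test on the later value counts all between-patient variation as noise, including the part that the earlier value predicts. Adjustment removes that part and costs one degree of freedom. For FIBTEM the dependence is partly built in, because the dose in the fibrinogen arm aims at each patient's own preoperative MCF.

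At stake is the width of the confidence intervals for the laboratory and ROTEM outcomes, which are named first among the secondary outcomes. Prespecification also matters: an adjustment chosen after the results are known invites doubt, and with two preoperative draws there is a choice of covariate to settle beforehand.

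**Working it through.** **1. The plan's own figure.** Table 1 gives 111 per group for a 70% reduction (difference 2.4 units, SD 5.9, two-tailed alpha 0.05, 80% power). A noncentral t calculation with the minimum Mann-Whitney relative efficiency, 0.864, returns 111, and 2 x 111 = 222, the recruitment target. This concerns the primary outcome and is not disputed. The documents give no power for any laboratory or ROTEM outcome.

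**2. General gain from adjustment.** N = 222, equal arms. Let rho be the correlation between the preoperative and the later value within arms. It is not in the documents, so a range is assumed. With one covariate,

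width ratio = sqrt[(1 - rho²)(1 + 1/(N - 4))] x t(219)/t(220), with t at 97.5%.

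The power column is for an outcome with exactly 80% power unadjusted, a difference of 0.378 SD at 111 per arm.

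| rho (assumed) | residual variance | width ratio | change in width | power |
|---|---|---|---|---|
| 0 | 1.00 | 1.002 | 0.2% wider | 80% |
| 0.3 | 0.91 | 0.956 | 4.4% narrower | 83-84% |
| 0.5 | 0.75 | 0.868 | 13.2% narrower | 90% |
| 0.7 | 0.51 | 0.716 | 28.4% narrower | 97% |

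Simulation of 6000 trials agrees. With HC3 standard errors the change is 0.9% wider at rho 0, and 3.7%, 12.6% and 28.0% narrower at the other three.

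**3. Which rows are plausible.** Eligibility confines preoperative fibrinogen to 1.0-3.8 g/l. Its SD is then at most 2.8/2 = 1.4 g/l, and 2.8/sqrt(12) = 0.81 g/l if uniform. A restricted range lowers correlation. Bypass, hemodilution and transfusion also come between the draws, and in intensive care "In case of a post-operative bleeding in CVICU the same algorithm (Figure 3) like in the OR will be used". The lower rows are therefore more plausible, and nothing in the documents supports 0.7 in particular.

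**4. FIBTEM MCF at 10 minutes.** The formula is dose = (preoperative MCF - on-bypass MCF) x weight/140, capped at 10 g, with a baseline of 12 mm or less replaced by 15 mm. Assumptions:
- on-bypass MCF is 10/22 of preoperative (the ratio in the plan's single worked example) plus noise of SD 1.5 mm (1.2 mm at means 18 and 15);
- weight 85 kg, SD 15;
- the rise exactly follows the formula (dose x 140/weight);
- preoperative values below 5 mm are excluded.

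In this model the slope on the preoperative value is near 1 in the fibrinogen arm and near 10/22 = 0.45 under placebo, hence robust standard errors. The narrowing of the interval for post-dose noise SD of 2/4/8 mm is:

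| preoperative mean | SD 4 mm | SD 3 mm | SD 2 mm |
|---|---|---|---|
| 22 mm | 33/16/5% | 25/10/3% | 14/5/1% |
| 18 mm | 31/14/4% | 25/10/3% | 16/5/1% |
| 15 mm | 22/9/3% | 17/6/2% | 11/4/1% |

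A separate rerun agreed to within about 1.5 percentage points. In the first cell, for example, the standard error falls from 0.499 to 0.337 mm: 1 - 0.337/0.499 = 32%, about the tabulated 33%. Adjusted and unadjusted differences agree within 0.02 mm, and coverage of the robust interval is 94.5-95.8%.

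The modelled difference between arms is about 8.4 to 12 mm, against unadjusted standard errors of about 0.34 to 1.15 mm. That is about 8 to 32 standard errors across the 27 settings. Later draws also depend on transfusion, which the model omits, so no FIBTEM figure is given for them.

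**5. Where a linear model does not fit.** Figure 1 defines CFT as the time until firmness reaches 20 mm. In the plan's dosing example the on-bypass FIBTEM MCF is 10 mm, so FIBTEM CFT would not exist for that sample. Unreached values would probably concentrate in the placebo arm.

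**6. HEPTEM.** The post-protamine draw has a 5-15 minute window, while the anesthesiologist and surgeon "complete a bleeding assessment ten minutes after the protamine is given". That lies inside the window, so the plan does not establish that this draw always precedes the study drug.

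**The case against.** The strongest case against is that a prespecified unadjusted t-test in a randomised trial is legitimate, and that the gain is either assumed or inconsequential. Every correlation is assumed, and the one trial-specific model rests on a single illustrative dosing example. Where that model applies, the difference is so many standard errors wide that a narrower interval decides nothing. All of this stands. It limits the point to an inexpensive gain in precision, but does not remove it, because the cost with no correlation is under 1%.

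Several stronger readings are tempting and are not supported:
- A reader might infer that the preoperative values go unused. They serve eligibility, dosing and arm comparison; what is missing is adjustment for them.
- A reader might infer that the t-tests are biased for want of a covariate. They are not. Selection does arise elsewhere: patients still bleeding after step 3 with FIBTEM above 20 mm drop out (Subject withdrawal criteria), and data unblinded before 24 hours are not analysed (Unblinding). Baseline adjustment repairs neither.
- A reader might take 80% to 97% as the trial's gain, or apply it to FIBTEM. It belongs to a hypothetical outcome with a 0.378 SD effect and an assumed correlation of 0.7.
- A reader might think that the nominal wording distorts a listed outcome. No listed secondary outcome is clearly multi-level nominal, and the word is probably a slip for ordinal.

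It can also be objected that ANCOVA for every ROTEM parameter is too sweeping. That is right for FIBTEM CFT and HEPTEM, and the change below is limited accordingly.

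**Conclusion.** The point holds as a modest improvement in precision for the continuous laboratory and ROTEM secondary outcomes. At 111 per arm the interval would narrow by about 4% to 28% for assumed correlations of 0.3 to 0.7, with the lower end more plausible, at a cost of 0.2% (0.9% with HC3) if the preoperative value predicts nothing. For FIBTEM MCF at 10 minutes the narrowing is about 1-33% under the stated assumptions; it sharpens the estimate without changing the conclusion. The primary analysis and N = 222 stand. The size depends on correlations that the documents do not give; the absence of any adjusted analysis does not, as it is plain from the text.

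**What to change.** Add a short paragraph to Details of the planned analysis:
- For each continuous laboratory variable, and each ROTEM parameter that has a preoperative value and is measurable in nearly all patients, report the ANCOVA-adjusted difference with 95% CI and robust standard errors at each post-dose time in Table 2 (10 minutes, end of surgery, 12 and 24 hours), with the preoperative value of the same variable as covariate.
- Name the preoperative draw (I or II) used for each variable, and state a rule for a missing baseline, such as the pooled mean of both arms.
- Leave HEPTEM unadjusted unless the Intraop II draw is confirmed to precede the study drug.
- Keep FIBTEM CFT out of the linear model and analyse it by ranks, with unreached values ranked last.
- Minor: in the rank-sum clause, correct nominal to ordinal.

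The cost is the paragraph and standard SAS code. No new samples, visits or patients are needed. One model per variable and time replaces one t-test, so the number of comparisons does not grow and no covariance structure has to be chosen. Preoperative fibrinogen and FIBTEM are needed for eligibility, so those baselines should be complete.
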